#### 3.1.2.1. Treatment Administration

[Figure 3.2](#) illustrates the order and timing of the treatments involved.

- Patritumab initial loading dose is 18 mg/kg IV (or placebo) over 60 minutes ( $\pm 10$  minutes) followed in cycle 2 and beyond with a maintenance dose of 9 mg/kg IV over 60 minutes ( $\pm 10$  minutes) every three weeks
  - Infusion time can be extended to a maximum of 120 minutes for subjects unable to tolerate the 60 minute infusion
- Cetuximab initial dose at 400 mg/m^2 IV as a 2-hour infusion followed by 250 mg/m^2 over 60 minutes weekly

One hour after the end of the cetuximab administration (on the weeks when cetuximab and platinum therapy are coadministered) infuse with either:

- Cisplatin at 100 mg/m^2 IV infused over 1 hour, every three weeks up to a maximum of 6 cycles
  - Pretreatment hydration with 2 liters of fluid prior to a cisplatin infusion is recommended and should adhere to institutional standards. Adequate hydration and urinary output must be maintained during the following 24 hours. Other pretreatments such as anti-emetic prophylaxis and post-treatments such as hydration are up to the discretion of the Investigator
  - This can be given in a separate infusion during patritumab and cetuximab infusion

[figure not shown]
OR

- Carboplatin, IV bolus over 30-60 minutes, every 3 weeks for a maximum of 6 cycles. The carboplatin dose will be calculated using the Calvert formula:
  - AUC 5 is the target
  - Carboplatin Dose (mg) = 5 x (glomerular filtration rate [GFR] + 25)
  - Estimated serum creatinine clearance (mL/min) calculated using the modified Cockcroft-Gault equation ([Appendix 17.1](#)) can also be used as an estimate for GFR

- The carboplatin dose is required to be re-calculated for every dosing based on the current GFR (or creatinine clearance as an estimate of GFR as per the protocol).
- Pre- and post-treatments are up to the discretion of the investigator

Note: It is important to use the infusion times given above for cisplatin and carboplatin; however, different infusion durations may be used if local practice dictates otherwise, except during Cycle 1, Day 1 for those subjects participating in the Intense PK sampling.

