A close monitoring of subjects, particularly during the first administration, is required. Special attention is recommended for subjects with reduced performance status and pre-existing cardiopulmonary disease.

When cetuximab is administered with platinum-based chemotherapy, the frequency of severe leukopenia or severe neutropenia may be increased and thus may lead to a higher rate of infectious complications such as febrile neutropenia, pneumonia, and sepsis compared to platinum-based chemotherapy alone.

If a subject develops an intercurrent illness (eg, infection) that, in the opinion of the Investigator and/or the Sponsor, mandates interruption of therapy, this intercurrent illness must resolve within a time frame such that no more than 2 consecutive cetuximab infusions are withheld.

When cetuximab is administered in combination with chemotherapeutic agents such as cisplatin or carboplatin, refer to their respective product information. Chemotherapy must not be administered earlier than 1 hour after the end of the cetuximab infusion.

Cetuximab therapy will not be delayed for cisplatin-related toxicity. Therefore, if the next infusion of cisplatin is delayed, the subject will continue to receive weekly infusions of cetuximab. In case of cetuximab-related toxicity, cisplatin will not be delayed and the planned schedule for administration should be maintained. If the cetuximab therapy is terminated for cetuximab-related toxicity, cisplatin will be continued. If there is cetuximab-related toxicity that does not resolve to Grade 0 or 1 (or baseline grade if higher than Grade 1), cetuximab will be discontinued at the discretion of the investigator.

Dose modifications for cetuximab are described in Table 5.3 and [Table 5.4](#).

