#### Study Treatment

Information for dosing and administration is found in Section 3.1.2 . Study drugs should be administered consecutively in the order below:

- Administer patritumab IV as specified in Section 3.1.2
- Administer cetuximab IV as specified in Section 3.1.2
- Administer cisplatin (or carboplatin) IV one hour after cetuximab, as specified in Section 3.1.2.

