#### End of Patritumab, Cetuximab, and Cisplatin or Carboplatin Infusions

- Perform vital sign measurement
- Record concomitant medications and AEs throughout administration of study drugs
- Sparse PK: collect a blood sample for PK at end of patritumab infusion (EOI) at 1 hr  $\pm$  10 min for all subjects (Table 8.1)
- Intense PK substudy

- Collect blood sample for PK at 3 hrs  $\pm$  10 min after start of patritumab infusion (approximately EOI for cetuximab) (Table 8.2)
- Collect blood sample for PK at 4 hrs  $\pm$  10 min after start of patritumab infusion (or 4.25 hrs  $\pm$  10 min, approximately EOI for carboplatin for those subjects receiving carboplatin) (Table 8.2)
- Collect blood sample for PK at 5 hrs  $\pm$  10 min after start of patritumab infusion) (approximately EOI for cisplatin for those subjects receiving cisplatin) (Table 8.2)
- Collect blood sample for PK at 6 hrs  $\pm$  10 min after start of patritumab infusion (Table 8.2)
- Collect blood sample for PK at 7 hrs  $\pm$  10 min after start of patritumab infusion (Table 8.2)

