**Table 8.2: Sub Study: Intensive PK Assessments Relative to the Start of Patritumab Infusion at Cycle 1 [n = 30]**

Study Treatment	Pre-inf	Day 1						Day 2	Day 3	Day 8	Day 15	Day 21
		1 h (EOI) $\pm$ 10 min	3 h $\pm$ 10 min	4 h $\pm$ 10 min	5 h $\pm$ 10 min	6 h $\pm$ 10 min	7 h $\pm$ 10 min	24 h $\pm$ 1 h	48 h $\pm$ 1 h	168 h $\pm$ 24 h	336 h $\pm$ 24 h	504 h $\pm$ 24 h
Patritumab	X	X	X	X	X	X	X	X	X	X	X	X
Cetuximab	X		EOI	X	X	X	X	X	X	X		
Cisplatin	X				EOI	X	X	X	X			
or												
Carboplatin	X			4.5 h EOI	X	X	X	X	X			

Pre-inf = Preinfusion, EOI = End of infusion, h = hours, min = minutes.

Note: One blood sample to produce 3 mL of serum sample will be collected at each time point. The resulting serum will be divided into 3 aliquots of 1 mL for analysis of each analyte depending on the dose regimen. Further details will be provided in the lab manual.

Patritumab will be infused over 1 hour followed by cetuximab infused over 2 hours (end of infusion at  $\sim$ 3 h) and then a 1 h pause ( $\sim$ 4 h). Then cisplatin will be infused over 1 hour (end of infusion  $\sim$ 5 h) or carboplatin infused over 30-60 minutes (end of infusion  $\sim$ 4.5 h). Subjects will remain in the clinic for hydration following cisplatin/carboplatin

infusions for approximately 2 hours following infusions to complete hydration (ie, ~7 h in total). Only one blood sample will be collected at each scheduled time point and the resulting serum will be aliquoted for each analyte. Blood collection should approximately correspond to EOI of each drug as listed, at the nominal times defined relative to the start of patritumab infusion.

Serum concentrations of patritumab, cetuximab, and platinum will be measured, as appropriate, using validated assays. Specific instructions for collection and shipping of PK samples will be provided in the Laboratory Manual.

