Similar as Table 15.4.1.3, will plot data by hours of 0, 3, 4, 5, 6, 7, 24, 48, and 168.

Figure 15.4.1.4 Mean Plasma Concentration of Cisplatin by Time from Intensive PK Sampling Pharmacokinetic Analysis Set

[figure not shown]
Similar as Table 15.4.1.4, will plot data by hours of 0, 5, 6, 7, 24, and 48.

Figure 15.4.1.5 Mean Plasma Concentration of Carboplatin by Time from Intensive PK Sampling Pharmacokinetic Analysis Set

Similar as Table 15.4.1.5, will plot data by hours of 0, 4.5, 5, 6, 7, 24, and 48.

Approved

Figure 15.4.2.1 Boxplot of Patritumab PK Parameters at Cycle 1 Pharmacokinetic Analysis Set

Source Data: adam.adpk; Listing 16.2.5.2.1

Programming Note: X-axis only presents one treatment group as Patritumab + cetuximab + cisplatin or carboplatin
 Y-axis presents AUC_{last} (ug.day/mL)

Programming Note: continue for HRG Low and Overall on the next page

The following figures follows Figure 15.4.2.1

[figure not shown]
Figure 15.4.2.2 Boxplot of Cetuximab PK Parameters at Cycle 1 by Treatment Pharmacokinetic Analysis Set

Figure 15.4.2.3 Boxplot of Cisplatin PK Parameters at Cycle 1 by Treatment Pharmacokinetic Analysis Set

Figure 15.4.2.4 Boxplot of Carboplatin PK Parameters at Cycle 1 by Treatment Pharmacokinetic Analysis Set

Approved

Figure 15.5.1.1 Plot of Cumulative Distribution Function of Change from Baseline on FACT-H&N HNS Score
 FACT-H&N Analysis Set

Source Data: adam.adqs; Listing 16.2.9.1, 16.2.9.2

Programming Note: x-axis will be displayed as follows: Cycle 2 Day 1 Change from Baseline; Cycle 3 Day 1 Change from Baseline; Cycle 5 Day 1 Change from Baseline and End-of-Treatment Change from Baseline. X-axis values will range from minimum change to maximum change depending on the data.

Display the legend for the two treatment groups: ○ Patritumab + cetuximab + cisplatin or carboplatin

[figure not shown]
□ Placebo + cetuximab + cisplatin or carboplatin

Figure 15.6.1 Heregulin (HRG) Distribution

Full Analysis Set

HRG High

Treatment: Patritumab + cetuximab + cisplatin or carboplatin

Source Data: adam.adxx

Programming Note: X-axis presents heregulin

Y-axis presents frequency (number of people with the heregulin range)

Programming Note: continue for Placebo + cetuximab + cisplatin or carboplatin and continue for HRG Low and Overall on the next page

Listing 16.2.1.1: Subject Disposition
 All Screen Subjects

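### Section 6.2.1 times the carboplatin end-of-infusion PK draw at 4.25 h, which is normally mid-infusion and conflicts with the 4.5 h in Table 8.2 and the SAP

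*Protocol*

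**What the plan says.** All times here count from the start of the patritumab infusion.

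- **Protocol Section 6.2.1** asks for a PK sample at 4 h ±10 min or, for carboplatin subjects, at 4.25 h ±10 min, described as "approximately EOI for carboplatin for those subjects receiving carboplatin". The bullet refers to Table 8.2.
- **Protocol Table 8.2** marks the carboplatin end-of-infusion (EOI) sample as 4.5 h, inside the column headed 4 h. The Section 8.1 text agrees: "or carboplatin infused over 30-60 minutes (end of infusion" at about 4.5 h). It adds: "Blood collection should approximately correspond to EOI of each drug as listed, at the nominal times defined relative to the start of patritumab infusion".
- **SAP Section 11.4**, for Figure 15.4.1.5, says: "Similar as Table 15.4.1.5, will plot data by hours of 0, 4.5, 5, 6, 7, 24, and 48".

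The rules that fix the clock on Cycle 1 Day 1 are these:

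- Section 6.2.1: "Study drugs should be administered consecutively in the order below" (patritumab, cetuximab, platinum).
- Section 3.1.2.1: patritumab over 60 ±10 min, extendable to 120 min if not tolerated; first cetuximab dose over 2 h; "Carboplatin, IV bolus over 30-60 minutes, every 3 weeks for a maximum of 6 cycles".
- Section 5.1.7.2: "Chemotherapy must not be administered earlier than 1 hour after the end of the cetuximab infusion".
- Section 3.1.2.1 lets local practice vary platinum infusion times, "except during Cycle 1, Day 1 for those subjects participating in the Intense PK sampling".

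**The concern.** Sites have two different times for one sample, and the SAP plots at the one that Section 6.2.1 does not give. The 4.25 h time also sits badly with the dosing rules, because carboplatin would usually still be running.

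The sample feeds a named parameter. The synopsis lists Cmax at end of infusion for platinum among the secondary PK parameters, and the abbreviation list defines Cmax as the highest concentration observed. SAP Section 8.4.2 log-transforms it and compares the arms by ANOVA to look for an interaction with patritumab. If a 30 min infusion is sampled at 4.25 h and next at 5 h, no sample falls at the peak.

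**Working it through.** **Inputs (minutes).** Patritumab 60 (range 50–70, or up to 120 if extended); cetuximab 120; pause at least 60; carboplatin 30–60. No gap is assumed between patritumab and cetuximab, since dosing is consecutive.

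**Formulas.** Carboplatin start = patritumab + 120 + 60. Carboplatin stop = start + carboplatin duration. Share of dose given at time t = (t − start) / duration, limited to 0–100%, assuming a constant infusion rate. Note that 4.25 h = 255 min and 4.5 h = 270 min.

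**Reproducing the plan's 4.5 h.** 60 + 120 + 60 + 30 = 270 min = 4.5 h. This matches Table 8.2, Section 8.1 and the SAP, for a 30 min infusion. The same sum for cisplatin, 60 + 120 + 60 + 60 = 300 min = 5.0 h, matches its scheduled EOI draw.

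**All permitted cases.**

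| Patritumab | Carboplatin | Start (h) | Stop (h) | Given at 4.25 h | Given at 4.5 h |
|---|---|---|---|---|---|
| 60 | 30 | 4.00 | 4.50 | 15/30 = 50% | 100% |
| 60 | 60 | 4.00 | 5.00 | 15/60 = 25% | 30/60 = 50% |
| 50 | 30 | 3.83 | 4.33 | 25/30 = 83% | 100% |
| 50 | 60 | 3.83 | 4.83 | 25/60 = 42% | 40/60 = 67% |
| 70 | 30 | 4.17 | 4.67 | 5/30 = 17% | 20/30 = 67% |
| 70 | 60 | 4.17 | 5.17 | 5/60 = 8% | 20/60 = 33% |
| 120 | 30 | 5.00 | 5.50 | 0% | 0% |
| 120 | 60 | 5.00 | 6.00 | 0% | 0% |

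**Trying to reproduce 4.25 h.** On the nominal schedule it needs a carboplatin infusion of 255 − 240 = 15 min. After the shortest patritumab infusion it needs 255 − 230 = 25 min. Both are below the 30 min minimum. Any gap between infusions only moves the stop later.

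**The ±10 min window.** It runs from 245 to 265 min (4.08–4.42 h). The earliest stop is 260 min, so the last 5 min can reach a stop. That requires patritumab and carboplatin together to take no more than 265 − 180 = 85 min, against a minimum of 80 and a nominal 90 or more. The nominal 30 min stop, at 270 min, lies 5 min after the window closes.

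**Effect on Cmax.** For a 60 min infusion without extension of patritumab, the stop falls at 4.83–5.17 h, which is exactly the window of the scheduled 5 h ±10 min draw, so the peak is still sampled. For a 30 min infusion on the nominal schedule the samples straddle the peak: one 15 min before the stop, the next 30 min after it.

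**The case against.** Other text largely points to the right time. The Section 6.2.1 bullet cites Table 8.2, footnote k of the schedule of events sends sites to that table, and the table, its text and the SAP all agree on 4.5 h. The laboratory manual, which is not among the documents, may settle it. The label also says approximately, with ±10 min. This stands as a limit on the consequence, but not as a defence of the number: Section 6.2.1 is an instruction to sites, and a site that follows it will normally draw during the infusion.

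Three stronger readings are tempting, and the documents do not support them.

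- *That a draw under Section 6.2.1 can never be an end-of-infusion sample.* The last 5 min of its window can be, when patritumab runs near 50 min and carboplatin near 30 min.
- *That Cmax is under-read by a known amount.* A one-compartment decay over the 0.5 h from stop to the 5 h draw gives a shortfall of 1 − 2^(−0.5/half-life). That is 29% for an assumed half-life of 1 h and 1.4% for 24 h. The documents give no half-life and do not say which platinum fraction is assayed, so no size is established.
- *That the interaction comparison is biased.* A proportional under-read common to both arms cancels in the geometric mean ratio. Nothing in this blinded design suggests that carboplatin infusion length differs by arm, so variation in it adds noise only. The comparison is also exploratory: SAP Section 8.4.2 gives 90% confidence intervals without acceptance bounds.

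**Conclusion.** The point holds as an error in an operative sampling instruction. The 4.25 h in Section 6.2.1 contradicts Table 8.2, Section 8.1 and the SAP. It precedes the nominal carboplatin stop by 15 min (30 min infusion) to 45 min (60 min infusion), and the earliest permitted stop by 5 min. The share of dose given at that time is nominally 50% or 25%, and ranges from 8% to 83% with patritumab at 50–70 min.

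The consequence is modest. A 30 min infusion can lose its observed peak, by an unquantified amount. A 60 min infusion keeps its peak, although its 4.25 h sample would be a mid-infusion value under an EOI label. Only carboplatin-treated subjects within the subset of about 30 are concerned, a number the documents do not state. PFS is unaffected. The result rests on the stated infusion durations being followed, no gap between patritumab and cetuximab, and a constant infusion rate. It should be corrected, but it does not threaten the trial's main conclusions.

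**What to change.** 1. In Section 6.2.1, replace 4.25 h with 4.5 h.
2. In Section 6.2.1 and Table 8.2, state that the carboplatin EOI draw is taken within ±10 min of the actual end of the carboplatin infusion. The number alone is not enough: a 45 min infusion stops at 60 + 120 + 60 + 45 = 285 min (4.75 h), outside both the 4.5 h window (4.33–4.67 h) and the 5 h window (4.83–5.17 h). With patritumab extended to 120 min, a 4.5 h draw would precede carboplatin altogether.
3. Add that if the stop falls within the window of another scheduled draw, that draw serves as the EOI sample and the 4 h draw is kept. For a 60 min infusion this is the 5 h draw. The rule also avoids near-duplicate samples, for example after a 55 min infusion (stop at 295 min, 4.92 h).

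Leave the cetuximab and cisplatin draws as they are. Moving them to actual stop times as well would create collisions: with patritumab at 120 min and cisplatin, cetuximab would end at 4 h and cisplatin at 6 h, on top of draws already scheduled there.

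The cost is wording in two places, plus sites noting the carboplatin stop time and knowing the planned infusion length before the 4 h draw. No samples are added.

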**6.2.2. Cycle 1: Week 1, Day 2**

- Intense PK substudy: collect blood sample for PK at 24 hrs  $\pm$  1hr after start of patritumab infusion (Table 8.2)

**6.2.3. Cycle 1: Week 1, Day 3**

- Intense PK substudy: collect blood sample for PK at 48 hrs  $\pm$  1hr after start of patritumab infusion (Table 8.2)

**6.2.4. Cycle 1: Week 2, Day 8**

- Physical examination
- Vital signs
- ECOG Performance Status
- Record concomitant medications and AEs
- Blood samples for CBC (hematology with differential and platelet count), (Section 9.7)-may be collected within 3 days prior to visit
- Serum chemistries-may be collected within 3 days prior to the visit
- Intense PK substudy: collect blood sample for PK at 168 hrs  $\pm$  24 hrs (Table 8.2)-within 3 days prior to visit
- Administer cetuximab IV (infused weekly) as specified in Section 3.1.2 (given on Day 8 and Day 15 of all cycles)

**6.2.5. Cycle 1: Week 3, Day 15**

- Physical examination
- Vital signs
- ECOG Performance Status

- Record concomitant medications and AEs
- Blood samples for CBC (hematology with differential and platelet count) (Section 9.7)-may be collected within 3 days prior to visit
- Serum chemistries-may be collected within 3 days prior to visit
- Intense PK substudy: collect blood sample for PK at 336 hrs  $\pm$  1 day (Table 8.2)
- Administer cetuximab IV (infused weekly) as specified in Section 3.1.2 (given on Day 8 and Day 15 of all cycles)

#### 6.2.6. Cycle 2 and 3

##### 6.2.6.1. Cycle 2, Day 1

- Collect blood samples for additional biomarkers

##### 6.2.6.2. Cycles 2 and 3, Day 1

#### Before Start of Patritumab Infusion

- Physical examination \*
- Vital signs \*
- Weight\*
- ECOG Performance Status
- At Cycle 3 only, perform an echocardiogram or MUGA scan (the same test must be used for a subject throughout the study)
- Record concomitant medications and AEs \*
- Have subject complete the PRO assessments before any study-related procedures are performed
- Collect blood sample for CBC with differential and platelet count\*
- Collect blood sample for serum chemistries \*
- For Cycle 2 Sparse PK: collect blood sample for HAHA/patritumab PK (Table 8.1).
- For subjects participating in the Intense PK substudy, the preinfusion patritumab PK sample is also the PK at 504 hrs  $\pm$  1 day (Table 8.2)
- At Cycle 3 Sparse PK: collect blood sample for PK at preinfusion and the patritumab EOI at 1 hr  $\pm$  10 min for all subjects (Table 8.2)
- Serum sample for HAHA

*Note: \* Can be collected on Days 8 and 15 at the discretion of the Investigator.*

### Study Treatment Administration

- Administer patritumab IV (infused once every 3 weeks) as specified in Section 3.1.2
- Administer cetuximab IV (infused weekly) as specified in Section 3.1.2
- Administer cisplatin or carboplatin IV (infused every 3 weeks, for a maximum of 6 cycles) as specified in Section 3.1.2

#### 6.2.7. Cycle 4 and all Subsequent Cycles, Day 1

##### 6.2.7.1. Day 1

- Physical examination\*
- Vital signs\*
- Weight\*
- ECOG Performance Status (Section 10.1)
- At visits for every third subsequent cycle (eg, Cycles 6, 9, 12 ...) conduct an echocardiogram or MUGA scan (the same test must be used for a subject throughout the study)
- Record concomitant medications and AEs\*
- Have subject complete the PRO assessments before any study-related procedures are performed
- Collect blood sample preinfusion for CBC with differential and platelet count\*
- Collect blood sample preinfusion for serum chemistries\*

*Note: \* Can be collected on Days 8 and 15 in Cycle 4 and all subsequent cycles at the discretion of the Investigator.*

### Study Treatment Administration

- Administer patritumab IV (infused once every 3 weeks) as specified in Section 3.1.2
- Administer cetuximab IV (infused weekly) as specified in Section 3.1.2
- Administer cisplatin or carboplatin IV (infused every 3 weeks, for a maximum of 6 cycles) as specified in Section 3.1.2

#### End of Cycle 6 and Every 4 Cycles

- Collect blood samples for additional biomarkers

#### 6.2.8. Every 6 Weeks

- Frequency of tumor assessments will be every 6 weeks to Week 24 ( $\pm 3$  days); every 12 Weeks ( $\pm 7$  days) thereafter

### **6.2.9. End of Study Treatment Visit (21 days after last dose)**

At the end of study treatment, the following procedures will be performed.

- Physical examination
- Vital signs
- Weight
- ECOG Performance Status (Section 10.1)
- Perform an echocardiogram or MUGA scan
- Perform a 12-lead ECG
- Record concomitant medications and AEs
- Have subject complete the PRO assessments before any study-related procedures are performed
- Collect blood sample for CBC with differential and platelet count
- Collect blood sample for serum chemistries
- Collect urine sample for urinalysis (Section 9.7)
- Sparse PK: collect a blood sample for PK (Table 8.1)
- Collect blood sample for HAHA
- Perform a serum or urine pregnancy test for female subjects of childbearing potential
- Tumor measurement assessments unless it was performed within the previous 6 weeks or the previous assessment demonstrated disease progression
- Collect blood samples for additional biomarkers

If there is a significant clinical or laboratory abnormality in need of monitoring beyond the end-of-study treatment visit, subjects will be followed until resolution of the abnormality, until it is considered stable, or the subject begins another cancer treatment.

For subjects with positive HAHA at the end-of-study treatment visit, additional serum samples for HAHA and PK should be collected every 3 months until HAHA titers return to baseline or until the start of another cancer therapy. Samples will be collected up to 1 year from the last dose of study drug or collected up to the time that a subject starts another cancer therapy, whichever occurs first.

### **6.2.10. 40 Days After Last Dose**

At 40 days after the last dose of any study drug administered, a telephone call will be placed to the subject to record AEs (See Section 4.1.5).

- Collect blood samples for additional biomarkers

